#### **4.3 Inclusion of Women and Minorities**

Both men and women and members of all races and ethnic groups are eligible for this trial.

#### **4.4 Recruitment and Retention Plan**

The following strategies will be applied to ensure complete enrollment within the first twelve months of study initiation:

MedStar Georgetown Transplant Institute is a network of multidisciplinary teams that provides medical care to participants with chronic liver disease. This network includes GUH, Washington Hospital Center (WHC), Franklin Square Medical Center, and MedStar Georgetown Transplant Institutes in Fairfax and Frederick. The network serves about 2,200 participants with chronic liver disease each year. [name] has weekly clinics at GUH, Franklin Square Medical Center, and MedStar Georgetown Transplant Institutes in Fairfax. [name] and [name] have weekly clinics at the GUH, WHC and MedStar Georgetown Transplant Institute in Frederick. When they identify potential candidates at any of the sites (pre-screen), eligible and interested subjects will be scheduled for a Screen 1 visit at GUH in DC and enrolled if indeed eligible at GUH. GUH is the site with the largest patient volume, will provide 70-80% enrollment for this study under MedStar Georgetown transplant Institute. The distance between GUH to other sites ranges from 5 to 17 miles (travel time 15 min to 40 min). These distances allow participants relatively easy travel from other MedStar sites to GUH, although only about 20-30% of enrollment under MedStar Georgetown Transplant Institute (GUH) will be referred from other MedStar sites. The transplant institute at Frederick is 45 miles from Georgetown (approx 1 hr drive), but due to the small patient volume seen the transplant institute at Frederick, and not many participants are expected to be referred to GUH. Therefore, the distance between GUH and the transplant institute at Frederick will have minimal impact on enrollment.

Among the 2,200 hepatology participants seen under the MedStar Network within one year, approximately 20% have compensated cirrhosis without liver cancer. Therefore we have a pool of 440 participants that meet the eligibility criteria for this study. Based on our small 50-patient survey, 90% of participants should be interested in participating in the study, despite having to undergo liver biopsy. Thus we have a pool of 400 participants per year from which to draw potential study candidates.

At the University of Puerto Rico, over 1000 participants are seen annually over the hepatology clinical enterprise. It is estimated that approximately 50% of these participants have underlying cirrhosis at different stages, including pre-transplant participants. [name] estimates that 10% of cirrhotic individuals may be eligible for the study translating to approximately 50-100 participants providing adequate numbers for screening into the study.

Monthly teleconferences will be arranged for Drs. [name], [name], [name], [name], [name], and the study coordinators to discuss enrollment and study related issues.

Our strategies are to prescreen most participants by medical record review after the protocol is approved, obtain consent, and, if needed, obtain a baseline biopsy from most participants within the first few months of study initiation so that candidates for intervention are identified quickly. From the pool of study candidates, we plan to screen 6 participants per month if possible. With this plan, even if there are delays for any reason, we will be able to complete the study within two years. We estimate 60% enrollment will occur at MedStar and 40% enrollment will occur at UPR.

We plan to allow up to three weeks from the day of biopsy to obtain the liver  $\gamma$ -OHPdG score. The liver samples will be batched and tested at least twice per month. If the rate of cirrhotic liver biopsies with a  $\gamma$ -OHPdG score  $\geq 3$  is lower than expected, we will increase the number of subjects that are pre-screened per month.

Participants will also be able to find trial details and sites through the Lombardi Cancer Center and Northwestern Cancer Prevention Consortium websites. In addition, the study investigators will work with advocacy groups across the country to improve awareness.

## 5. AGENT ADMINISTRATION

Polyphenon E will be administered on an outpatient basis. Reported AEs and potential risks are described in Section 6.2.

### 5.1 Dose Regimen and Dose Groups

The treatment to be used in this trial is outlined below in Table 3:

**Table 3:** Trial Treatment

| Drug         | Dose/
Potency | Dose
Frequency | Route of
Administration | Regimen/
Treatment
Period | Use          |
|--------------|------------------|-------------------|----------------------------|---------------------------------|--------------|
| Polyphenon E | 400 mg EGCG      | daily             | oral                       | Continuously
for 24 weeks    | Experimental |
|              | 400mg EGCG       | bid               |                            |                                 |              |
|              | 600mg EGCG       | bid               |                            |                                 |              |
|              | 800mg EGCG       | bid               |                            |                                 |              |
|              | 1000mg EGCG      | bid               |                            |                                 |              |

On an outpatient basis, Polyphenon E will be administered orally according the dose level of

EGCG assigned for each cohort on a continuous dosing schedule for 24 weeks.

The medication will be released on Visit 1 (week 1, day 1); and Visit 2 (week 13 +/- 3 days). A participant diary will be provided to participants and collected from them by the study coordinator approximately every 12 weeks during clinic visits for the 24 weeks of treatment. Thus participants will have their diary reviewed and a pill count performed at their Visit 2 (week 13 +/- 3 days) and at Visit 3 (end of intervention, 25 +/- 3 days).

## **5.2 Polyphenon E Administration**

The study agent will be self-administered by the subject. Participants will be instructed to take each dose of Polyphenon E after a light meal.

The medication will be released by the research pharmacies at GUH or UPR every 12 weeks; thus on Visit 1 (week 1, day 1), and Visit 2 (week 13 +/- 3 days). A participant diary will be provided. In order to give participants some flexibility for Visit 2 (week 13 +/- 3 days), patient will be provided one extra week of medication, so they will not run out of medication before they receive the medication on Visit 2 (week 13 +/- 3 days). Participants will have their diary reviewed and a pill count performed at their Visit 2 (week 13 +/- 3 days) and Visit 3 (end of intervention, week 25 +/- 3 days).

Polyphenon E/EGCG will be administered orally at a doses of 400 mg qd, 400 mg bid, 600 mg bid, 800 mg bid, 1000 mg bid on a continuous dosing schedule for a total of 24 weeks, according to the dose escalation 3 + 3 design. Participants are instructed to take their medication after a light meal. The meal should not include either milk or juice during the meal. If a dose is missed, the participant should not make up the missing dose the next day, as this would result in an extra dose for that day. Participants should not make up vomited doses. The missing dose or vomited dose should be recorded in the medication diary.

### **Pharmacokinetics study:**

The day before the pharmacokinetic study (Visit 1), study participants at Georgetown University are instructed to fast after midnight except for drinking water. On the pharmacokinetic study day, study subjects at Georgetown University skip breakfast and take no over the counter medications, vitamins, or health food products. Study participants at Georgetown University come to the clinic in the early morning (6–8 a.m.) and are provided with food for breakfast. Immediately after or during breakfast, study subjects swallow their Polyphenon E capsules with a glass of water. Study subjects are allowed unlimited water intake throughout the study day. Other drinks are not allowed. Blood samples (5–7 ml each) are collected before the administration of the Polyphenon E and then at time points 1.5, 3.5, and 8.5 hours (+/- 5 minutes) after drug administration. Study subjects self-collect urine before dosing and at each PK blood draw. After the 3.5 h blood collection, food for lunch is provided to the study subjects.

## **5.3 Run-in Procedures**

Not applicable

## 5.4 Contraindications

Participants who consume 3 or more cups of green tea per day, or take vitamins or health food products that are labelled as containing green tea components.

## 5.5 Concomitant Medications

Medications specifically prohibited in the exclusion criteria are not allowed during the ongoing trial.

### Acceptable Concomitant Medications

All treatments that the investigator considers necessary for a subject's welfare may be administered at the discretion of the investigator in keeping with the community standards of medical care. All concomitant medication will be recorded on the case report form (CRF) including all prescription, over-the-counter (OTC), vitamin and mineral supplements, herbal supplements, and IV medications and fluids. CRF reporting will include: 1) start and stop date, dose and route of administration, and indication. Medications taken for study procedures (e.g. biopsy) will not be included. If changes occur during the trial period, documentation of drug dosage, frequency, route, and date should also be included on the CRF.

All concomitant medications received starting at Screen 1 or within 28 days of the first dose of trial treatment (whichever is earlier) and at every clinic visit should be recorded.

### Prohibited Concomitant Medications

Subjects are prohibited from receiving the following therapies during the Screening and Treatment Phase (including retreatment for post-complete response relapse) of this trial:

- Investigational agents other than Polyphenon E
- Medications listed as prohibited in the trial Exclusion Criteria (Section 4.2).

Participants must be willing to refrain from drinking > 3 cups of green tea daily, or take supplements or foods that are labelled as containing green tea during the screening, intervention, and follow-up periods

There are no restrictions on other caffeine-containing beverages or over-the-counter medications.

## 5.6 Dose Interruption and Modification

Guidelines for Dose Interruption of Polyphenon E provided below are based on the National Cancer Institute Common Terminology Criteria for Adverse Events (NCI-CTCAE Version 4.0) and the Hepatotoxicity Assessment Algorithm.

For any non-liver related toxicities, Polyphenon E can be continued for grade 1 adverse events attributed by an investigator to be possibly, probably, or definitely related to treatment.

Polyphenon E will be held for grade 2 adverse events attributed by an investigator to be possibly, probably, or definitely related to the treatment. In this case, Polyphenon E will be held until the adverse reaction resolves or improves to baseline, at which time Polyphenon E can be re-initiated at the same dose level. If the adverse reaction re-occurs at grade 2, Polyphenon E should be

permanently discontinued. Polyphenon E will be discontinued for grade 3 or 4 adverse events attributed by an investigator to be possibly, probably, or definitely related to the treatment.

Polyphenon E will be held for any elevation in liver function tests and investigators will determine the course of action according to Hepatotoxicity Assessment Algorithm (Appendix D) for details.

Hepatotoxicity Assessment Algorithm (**Appendix D**) is being used for hepatotoxicity safety monitoring, in conjunction with NCI CTCAE which is used for grading of adverse events. We will monitor participants' laboratory parameters every 1-2 weeks as recommended. Participants who do experience toxicity should be reassessed within 3-4 days of the toxicity for resolution. Regarding hepatotoxicity, the procedures for laboratory monitoring, treatment interruption, preinitiation, or permanent discontinuation are described in detail in Appendix D.

There is no plan for dose modification after patient has started Polyphenon E treatment.

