Cirrhotic participants are likely to have a baseline increase in transaminases. We deduce this from the fact that most participants are found to have cirrhosis only after having a blood test for an unrelated condition (such as chronic viral hepatitis, non-alcoholic steatohepatitis, or alcoholic liver disease) that causes elevated transaminases. A mild increase ( $</= 2.5 \times$  upper normal level (UNL)) in transaminase does not reflect the level of liver function impairment in well-compensated cirrhosis. To ensure safety, subjects selected will have normal direct bilirubin, and synthetic function including albumin  $\geq 3.0 \text{ g/dL}$  and INR  $\leq 1.3$ . Following FDA recommendations, weekly or bi-weekly (depending on assigned dose, clinical stability, and liver biochemical stability of the participant) liver function & coagulation tests will be carried out for safety monitoring. We propose to enroll participants with baseline AST/ALT that is less than  $2.5 \times$  UNL. Change of transaminase levels from baseline will be used to monitor the hepatotoxicity of Polyphenon E. In participants who develop changes in transaminases, we will hold treatment until levels recover to baseline OR discontinue therapy based on the extent of the increase of AST/ALT from the baseline level, according to the detailed dose modification/withholding drug scheme for elevated ALT/AST described in Section 5.6.

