- h. In between Visits 1 and 2, and between Visits 2 and 3, liver function & coagulation tests including AST, ALT, alkaline phosphatase, total protein, albumin, direct bilirubin, indirect bilirubin, total bilirubin, magnesium, GGT, calcium, phosphorus, and INR will be performed according to the schedule below. These tests will be performed at the central lab, or, if the participant prefers, at a local clinic lab. Participants who experience hepatotoxicity according to Appendix D will be re-evaluated every 3-4 days until resolution.
  - a. For participants assigned to 400 mg EGCG QD or 400 mg EGCG BID: bi-weekly liver function & coagulation testing (every 14 +/- 3 days).
  - b. For participant assigned to  $\geq$ 600 mg EGCG BID: weekly liver function & coagulation testing (every 7 +/- 3 days) for the first 2 weeks on agent, or until the participant demonstrates stability of clinical condition and liver biochemical enzymes\* for at least 2 weeks, whichever is longer. Thereafter, the participant will receive bi-weekly liver function & coagulation testing (every 14 +/- 3 days).

\*Stability of clinical condition and liver biochemical enzymes is defined as meeting all of the following, as listed in Appendix D:

- a. No symptoms of clinical hepatitis (vomiting, nausea, right upper quadrant pain)
- b. No ALT or AST increases to  $\geq$ 5x upper limit of normal
- c. No ALT or AST increases to  $\geq$ 3x baseline levels
- d. No elevations in direct bilirubin  $>$  1.5 ULN
- e. No elevation of direct bilirubin  $>$  ULN, regardless of ALT or AST levels, with indicators of immunological reaction (i.e., rash or  $>$ 5% eosinophilia).

- i. For details on the Child-Pugh score, see [https://www.qxmd.com/calculate/calculator\\_43/child-pugh-score](https://www.qxmd.com/calculate/calculator_43/child-pugh-score).
- j. Only the subjects with  $\gamma$ -OHPdG-high in the base-line liver biopsy will be registered for treatment. The treatment is to start within 14 days from registration. The subjects with  $\gamma$ -OHPdG-low liver

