|   | (every 7 +/- 3 days) until the participant demonstrates stability* for at least 2 weeks. Thereafter, the participant will receive bi-weekly liver function & coagulation testing (every 14 +/- 3 days). |
| 
* Stability of clinical condition and liver biochemical enzymes is defined as meeting all of the following, as listed in Appendix D:
 

a. No symptoms of clinical hepatitis (vomiting, nausea, right upper quadrant pain)

b. No ALT or AST increases to <math>\geq 5</math>x upper limit of normal

c. No ALT or AST increases to <math>\geq 3</math>x baseline levels

d. No elevations in direct bilirubin <math>> 1.5 \times</math> ULN.

e. No elevation of direct bilirubin <math>></math> ULN, regardless of ALT or AST levels, with indicators of immunological reaction (i.e., rash or <math>> 5\%</math> eosinophilia).

 |   |

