### **8.3 Off-Agent Criteria**

Participants may stop taking study agent for the following reasons: completed the protocol-prescribed intervention, AE or serious adverse event (SAE) (see section 5.6, Appendix D), inadequate agent supply, noncompliance, concomitant medications, or medical contraindication. Participants will continue to be followed, if possible, for safety reasons and in order to collect endpoint data according to the 7.1 SCHEDULE OF EVENTS.

For any non-liver related toxicities, Polyphenon E will be held for grade 2 adverse events attributed by the treatment until the adverse reaction resolves or improves to baseline, at which time Polyphenon E can be re-initiated at the same dose level. If the adverse reaction re-occurs at grade 2, Polyphenon E should be permanently discontinued.

Hepatotoxicity Assessment Algorithm (**Appendix D**) is being used for hepatotoxicity safety monitoring, in conjunction with NCI CTCAE which is used for grading of adverse events. We will monitor participants' laboratory parameters every 1-2 weeks as recommended, according to protocol section 7. Regarding hepatotoxicity, the procedures for laboratory monitoring, treatment interruption, preinitiation, or permanent discontinuation are described in detail in Appendix D.

If the participant meets at least one criterion of Appendix D, but close monitoring of a participant is not possible, the participant will be taken off agent.

If the participant meets any Discontinue Therapy Criteria, the participant will be taken off agent. DTC is defined as:

- a. Grade 3 or higher toxicity based on CTCAE criteria which is possibly, probably, or definitely related to the study agent OR
- b. Requires discontinuation of treatment based on the Hepatotoxicity Assessment Algorithm (Appendix D) OR
- c. Any hepatic decompensation such as
  1. New onset ascites or worsening of ascites (requiring increase in drug therapy or requiring surgical intervention such as paracentesis).
  2. Variceal bleeding documented by endoscopy
  3. Spontaneous bacterial peritonitis documented by positive culture
  4. Hepatic encephalopathy
  5. Hepatorenal syndrome (Type 1 or 2)
  6. Porto-pulmonary hypertension
  7. Hepato-pulmonary hypertension
  8. Any liver related event that leads to hospitalization or G4 event.

Participants taken off-agent due to adverse event will be followed until resolution of the adverse event or until stabilization of labs and the participant's clinical picture.

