**APPENDIX D**  
**Hepatotoxicity Assessment Algorithm**

| Baseline ALT or AST             | Liver toxicities  | Treatment and follow up plan   |
|---------------------------------|---|--|
| Normal                          | ALT or AST increases to $\geq 5$ x upper limit of normal AND no liver related symptoms (nausea, vomiting, right upper quadrant pain)  | Repeat liver profile (AST, ALT, bilirubin (total, direct, and indirect) and INR) within 3 to 4 days. Email NCPC and the protocol PI within 48 hours of learning about the event ( [contact] and [contact] ).   |
| Elevated                        | ALT or AST increases to $\geq 3$ x baseline levels AND no liver related symptoms (nausea, vomiting, right upper quadrant pain)  | Interrupt the study medication. Initiate potential DILI work-up for competing etiologies, repeat liver profile and INR within 48-72 hours. Study medication can be restarted only if a firm competing etiology is identified and liver tests return to baseline. Email NCPC and the protocol PI within 48 hours of learning about the event ( [contact] and [contact] ). |
| Irrespective of baseline levels | ALT or AST increase to $\geq 3$ x baseline AND symptoms of clinical hepatitis (vomiting, nausea, right upper quadrant pain)   | Interrupt the study medication. Initiate potential DILI work-up for competing etiologies, repeat liver profile and INR within 48-72 hours. Study medication can be restarted only if a firm competing etiology is identified and liver tests return to baseline. Email NCPC and the protocol PI within 48 hours of learning about the event ( [contact] and [contact] ). |
| Irrespective of baseline levels | Elevations in direct bilirubin $> 1.5 \times$ ULN, and if ALT or AST $\geq 3$ x baseline but without liver related symptoms (vomiting, nausea, right upper quadrant pain)   | Interrupt the study medication. Initiate potential DILI work-up for competing etiologies, repeat liver profile and INR within 48-72 hours. Study medication can be restarted only if a firm competing etiology is identified and liver tests return to baseline. Email NCPC and the protocol PI within 48 hours of learning about the event ( [contact] and [contact] ). |

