  - *Repeat liver profile (AST, ALT, Bilirubin (total, direct, and indirect)) and INR within 3 to 4 days. Monitor the patient as per “close observation” definition in the DILI guidance.*
- When the ALT or AST are elevated at baseline and increase to  $\geq 3$ x baseline during the trial **AND** the patient does not have liver related symptoms (nausea, vomiting, right upper quadrant pain) then
  - *Interrupt the study medication. Initiate potential DILI work-up for competing etiologies, repeat liver profile and INR within 48-72 hours, and place patient under “close observation” as defined in the DILI guidance. Study medication can be restarted only if a firm competing etiology is identified and liver tests return to baseline.*
- When the ALT or AST increase to  $\geq 3$ x baseline (irrespective of baseline levels) during the trial and are associated with symptoms of clinical hepatitis such as vomiting, nausea, right upper quadrant pain), then
  - *Interrupt the study medication. Initiate potential DILI work-up for competing etiologies, repeat liver profile and INR within 48-72 hours, and place patient under “close observation” as defined in the DILI guidance. Study medication can be restarted only if a firm competing etiology is identified and liver tests return to baseline.*

2. For patients with elevations in direct bilirubin  $> 1.5 \times$  ULN, and if ALT or AST  $\geq 3 \times$  baseline but without liver related symptoms (vomiting, nausea, right upper quadrant pain) then

- *Interrupt the study medicine. Initiate potential DILI work-up for competing etiologies, repeat liver profile and INR within 48-72 hours, and closely observe the patient. For “close observation” of patients, refer to the DILI guidance. Study medication can be restarted only if a firm competing etiology is identified and the liver tests return to baseline.*

3. With any elevation of direct bilirubin  $>$  ULN, regardless of ALT or AST levels, and in the presence of indicators of immunological reaction (i.e., rash or  $> 5\%$  eosinophilia), or appearance of nausea, vomiting, right upper quadrant pain (symptoms consistent with clinical hepatitis) then

- *Permanently discontinue study medication. Initiate potential DILI work-up for competing etiologies, repeat liver profile and INR within 48-72 hours, and place patient under “close observation” as defined in the DILI guidance.*

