#### **Close observation:**

1. Interrupt the investigational agent administration
2. Repeat liver biochemistries and additional testing within 24-72 hrs

 (refer to the “Guidance for Industry : Drug induced liver injury (DILI): Premarketing clinical evaluation” <http://www.fda.gov/downloads/Drugs/.../Guidances/UCM174090.pdf>)

3. Monitor patient twice or thrice a week until liver biochemistries (ALT, AST, alkaline phosphatase, bilirubin (total, direct, and indirect), and coagulation profile [INR]) resolve, stabilize or return to within baseline values
4. Monitor liver biochemistries once a week if abnormalities stabilize and the patient is asymptomatic
5. Obtain a detail history for symptoms assessment: appearance or worsening of clinical symptoms of hepatitis (fatigue, nausea, vomiting, right upper quadrant pain or tenderness, fever, rash or eosinophilia). If a patient is symptomatic, the drug must be discontinued immediately and a potential DILI evaluation must be performed.
6. Obtain a more detailed history of symptoms and prior or concomitant diseases;
7. Obtain a history for concomitant medications, acetaminophen, dietary supplements, herbal remedies, other over the counter medications, recreational drug use, and special diets
8. If possible quantify the alcohol consumption to assess for alcoholic hepatitis
9. Obtain a history of exposure to environmental chemical agents.
10. If INR is also elevated, a trial of intravenous vitamin K administration may be considered, especially in cholestatic patients.

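### Appendix D gives two different restart rules after liver injury, and its table omits the drug interruption that its narrative calls for at 5 x ULN

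*Combined protocol and SAP*

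**What the plan says.** **Which text governs.** Section 5.6 sets the hold and sends the decision to Appendix D: "Polyphenon E will be held for any elevation in liver function tests and investigators will determine the course of action according to Hepatotoxicity Assessment Algorithm". Section 8.3 says that "the procedures for laboratory monitoring, treatment interruption, preinitiation, or permanent discontinuation are described in detail in Appendix D". Section 2.5.2 gives the reference point, "Change of transaminase levels from baseline will be used to monitor the hepatotoxicity of Polyphenon E". It goes on to say that drug is held until levels are back at baseline, or stopped, depending on how large the rise is, and refers to Section 5.6 for the scheme.

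**Restart.** Three rows of the Appendix D table, and the matching items in the numbered narrative below it, make restart conditional on two things together: a definite other cause, and liver tests back at baseline. The re-initiation sentence in the Follow-Up Procedures, near the end of the appendix, accepts any one of three outcomes: the abnormalities level off, go back to their pre-trial values, or become normal. It does not ask for another cause.

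**Normal baseline, 5 x ULN or more, no symptoms.** The table row says "Repeat liver profile (AST, ALT, bilirubin (total, direct, and indirect) and INR) within 3 to 4 days" and asks for an email within 48 hours. The narrative for the same case says "Repeat liver profile (AST, ALT, Bilirubin (total, direct, and indirect)) and INR within 3 to 4 days. Monitor the patient as per" the definition of close observation. The first item in Appendix D's own Close observation list is "Interrupt the investigational agent administration".

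**Rise to 3 x baseline with hepatitis symptoms.** The table and narrative interrupt drug and leave restart open. Item 5 of the Close observation list says instead that drug is to be discontinued at once in a symptomatic participant. Limb (b) of the Discontinue Therapy Criteria (DTC, Sections 3.1 and 8.3) is met when Appendix D calls for discontinuation.

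**The concern.** The trial gives a green tea extract to people with cirrhosis, and the agent's class carries reports of liver injury. Section 6.2 records positive rechallenge and liver failure with other green tea extracts, while saying that such severe reactions have not been reported with Polyphenon E. Whether to give drug again after an unexplained rise is therefore the most safety-relevant decision in Appendix D, and the appendix answers it in two ways. The looser answer permits rechallenge when no other cause has been found.

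The second conflict concerns whether a participant at 5 x ULN keeps taking drug while the tests are repeated. A site working from the table and a site working from the narrative could treat the same result differently.

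There is also a link to dose escalation, because DTC limb (b) depends on what Appendix D is taken to call for. An interrupted participant with no other cause found cannot restart under the strict rule, so has in effect been discontinued. Under the loose rule the same participant could resume.

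**Working it through.** The plan states no figure to reproduce here; the check is a comparison of texts.

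| Situation | Appendix D table | Numbered narrative | Close observation or Follow-Up Procedures | Section 5.6 |
|---|---|---|---|---|
| Restart after interruption | Other cause found and tests at baseline | Same | Levelled off, or at pre-trial values, or normal | Defers to Appendix D |
| Normal baseline, 5 x ULN or more, no symptoms | Repeat tests, email | Repeat tests, close observation | Close observation item 1: interrupt | Hold |
| 3 x baseline or more, with symptoms | Interrupt, restart possible | Same, plus close observation | Close observation item 5: discontinue | Hold |

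**Step 1, restart.** Two facts matter: whether another cause was found, and whether tests are back at baseline or have only levelled off above it. That gives 2 x 2 = 4 combinations.

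| Other cause found? | Tests | Table and narrative | Follow-Up Procedures |
|---|---|---|---|
| Yes | At baseline | Restart allowed | Restart allowed |
| Yes | Levelled off above baseline | Not allowed | Restart allowed |
| No | At baseline | Not allowed | Restart allowed |
| No | Levelled off above baseline | Not allowed | Restart allowed |

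The rules agree in 1 of 4 combinations and disagree in 3. They also reach the same people. The rows with the strict rule start a work-up for drug-induced liver injury (DILI), and the loose sentence comes at the end of the follow-up procedures for participants having that work-up. It stands directly after the tests required for those who meet both the ALT and bilirubin stopping criteria or have clinical symptoms.

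**Step 2, the 5 x ULN row.** The table has five rows. Three interrupt drug, one stops it permanently, and this one gives neither instruction. The narrative reaches an interruption through close observation, and Section 5.6 reaches a hold directly. The table row is the odd one out.

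**Step 3, symptomatic rise to 3 x baseline.** Appendix D lists its off-agent criteria after the table and repeats them at the end as grounds for permanent discontinuation. They are: close monitoring not possible; direct bilirubin above ULN with immune signs or hepatitis symptoms; recurrence on rechallenge; and hepatic decompensation. A first symptomatic rise to 3 x baseline with normal direct bilirubin is not among them. The list therefore supports reading item 5 as an interruption, though the word used there is discontinue.

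**The case against.** **On the two conflicts.** The strict restart rule is specific and the later sentence is general and permissive, so the specific rule could be taken to prevail. The 5 x ULN row has no restart rule of its own, and the general sentence might be meant for it. That row is also silent rather than contrary: nothing tells the site to continue drug, and Section 5.6 holds it. Every row requires an email to the consortium and protocol PI within 48 hours, which limits divergence between sites, and Section 8.5 adds study-level holds.

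Part of this stands. A careful reader can reach the safer action in both cases, and central notification helps. But no sentence says which restart rule prevails, and the general one cannot be confined to the 5 x ULN row because it closes the follow-up for the more serious cases as well. With interruption written into the three neighbouring rows, its absence from this one is easily read as deliberate.

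**Stronger readings that a reader might infer.**

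- *Smaller rises have no rule.* Appendix D has no row for an asymptomatic transaminase rise, with normal direct bilirubin, below 5 x ULN (normal baseline) or 3 x baseline (elevated baseline). At the entry limit of 2.5 x ULN the latter is 3 x 2.5 = 7.5 x ULN. But Section 5.6 holds drug for any elevation and calls for reassessment in 3 to 4 days, and Section 2.5.2 supplies the hold until recovery to baseline. The weakness is only that this rule is not stated in Section 5.6, where Section 2.5.2 says the detail is.
- *Section 7 lets drug continue below those limits.* It says "Stability of clinical condition and liver biochemical enzymes is defined as meeting all of the following, as listed in Appendix D", and then "Thereafter, the participant will receive bi-weekly liver function & coagulation testing". These words set how often blood is tested. They do not say that drug continues.
- *DTC limb (b) cannot be applied.* The off-agent list gives it a workable meaning.
- *Section 6.2 adds a competing rule.* Its withhold-or-discontinue sentence follows an FDA recommendation, in a section on reported events and risks.

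**Conclusion.** Appendix D contradicts itself on restart, and its table disagrees with its narrative on interruption at 5 x ULN from a normal baseline. The word used for symptomatic participants is a lesser ambiguity, which the off-agent list largely resolves. These are drafting faults in safety rules. They do not show that the liver rules as a whole cannot be followed.

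The practical effect is small. Enrollment stopped with 13 treated, no MTD was established, and safety is summarized descriptively. The recorded DTC count (1 of 4 in cohort 4, none in cohorts 1 to 3) does not change. The documents do not say how many of the 13 met either situation, so the number lies somewhere from 0 to 13. It should not be inferred that anyone was wrongly restarted or kept on drug. The value lies in the record and in any successor trial, since Sections 8.1 and 13.4 suggest dose level 3 as a future starting dose and these rules may be reused.

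One assumption is needed: that the Close observation list printed in Appendix D is what the narrative means by that term. The narrative cites outside guidance for the definition, and this review does not rely on that guidance.

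**What to change.** 1. In the Follow-Up Procedures of Appendix D, replace the re-initiation sentence with the stricter rule already in the table and narrative, so that restart always needs both a definite other cause and tests back at baseline.
2. Add an instruction to interrupt study drug to the table row for a normal baseline rising to 5 x ULN or more without symptoms.
3. In Close observation item 5, change discontinued to interrupted unless an off-agent criterion in Appendix D is met. DTC limb (b) is then unambiguous.
4. Keep the hold for any elevation in Section 5.6, and write into it the Section 2.5.2 rule to hold until levels recover to baseline, for rises below the Appendix D triggers. Dropping the hold for smaller rises would remove the most protective rule in the plan and run against both Section 2.5.2 and the FDA recommendation relayed in Section 6.2.

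The cost is four wording changes. The sample size, the recorded DTC count, the laboratory schedule and the biomarker analysis stay as they are, and the clinical thresholds remain for the sponsor to set.
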